6.6 Locations/Facilities

Phase 1: Interviews/focus groups, if able to be scheduled in-person, will be conducted at the CHC in a private room. Our clinic locations are Fair Haven Community Health Center in New Haven and Norwalk Community Health Center in Norwalk, CT. Interviews/focus groups may also be conducted by phone or ZOOM. We will provide participants access to ZOOM and instructions how to use it, if they are not familiar with this platform.

Phase 2: Data collection will be collected from participants in-person at the clinic or private location preferred by participants or via telehealth for study questionnaires. A1C data will be collected at the clinic or private location preferred by participants. Electronic health record and patient portal data will be collected by trained clinic personnel at each clinical site.

7 Statistical Design

7.1 Sample Size Considerations

Phase 1: Not applicable

Phase 2: Since this is a pilot study to provide preliminary data for a future large study, we conducted a power analysis to show an effect size on A1C using a feasible sample size of 30 participants. We chose the more conservative approach to power on A1C vs. portal logins as we anticipate a smaller effect size on A1C. In our recent study with low-income Latinx adults, we obtained a standard deviation of 1.2 and a sample correlation of 0.57 in repeatedly measured A1C over 6 months. The estimated standard deviation of changed A1C will be 0.72 and the sample size of 30 will produce a standard error of 0.13. Therefore, the proposed sample size of 30 could estimate a change of A1C over time with a margin of $\pm 0.27\%$ A1C for 95% confidence interval.

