7.2 Planned Analyses

Phase 1 analysis:

The sample of participants in the interviews/focus groups will be described using frequency distributions and appropriate summary statistics (SAS version 9.4). Content analysis will be used to analyze qualitative data from each type of stakeholder along with field notes and interviewer observations (Hsieh, 2005) Rigor for this process includes: (a) transcribing taped interviews; (b) checking transcripts against tapes for accuracy; (c) developing coding categories by two members of the research team; (d) assigning codes of text with appropriate checks; (e) reviewing coded data to identify themes across participants; and (f) a team approach to data analysis. At research team meetings we will assess researcher bias, coding saturation, and interpretative congruence. Results will be used to finalize the intervention protocol for implementation in Phase 2

Phase 2 Analysis: Data will be collected in the form of questionnaires online on the secure REDCap system. A1C data, electronic medical record data and patient portal data will be entered into REDCap or Excel and merged into one database. All data that are downloaded from REDCap or Excel will be onto a Yale server, which has several secure firewall systems. Descriptive analyses will be performed to assess demographic and clinical characteristics of the sample. Feasibility data will be summarized. Distributions of outcome variables will be examined for central tendency and dispersion. We will estimate the Cohen's D effect size of MAP on A1C and will examine the intervention effect over 6 months using generalized linear mixed model (GLMM) with random intercept, which will incorporate the correlation within repeatedly measured A1C. The slope of time will represent the average change of A1C over 6 months. The GLMM will include all participants with data at baseline and at least one of post-intervention value and will handle missing data using maximum likelihood approach. To confirm findings with missing data, we will rerun the GLMM with multiple imputations which will be produced by assuming multivariate normal distribution of repeatedly measured A1C. Number of logins and the repeatedly measured secondary outcomes will be analyzed with the same approach using the GLMM. Residuals will be assessed for normality assumption and

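### Section 7.1: the SD of A1C change (0.72), its SE (0.13) and the ±0.27% margin do not follow from the stated SD of 1.2 and correlation of 0.57, which give about 1.11, 0.20 and ±0.42%

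*Combined protocol and SAP*

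**What the plan says.** Section 7.1 (Sample Size Considerations) sets the Phase 2 sample at 30 on grounds of feasibility and describes its calculation as one "to show an effect size on A1C using a feasible sample size of 30 participants". The inputs come from the investigators' recent study in low-income Latinx adults: "we obtained a standard deviation of 1.2 and a sample correlation of 0.57 in repeatedly measured A1C over 6 months". The next sentence is "The estimated standard deviation of changed A1C will be 0.72 and the sample size of 30 will produce a standard error of 0.13". The section concludes that "the proposed sample size of 30 could estimate a change of A1C over time with a margin of" ±0.27% A1C at 95% confidence. It gives no formula, no separate SDs for baseline and 6 months, and no allowance for dropout.

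Section 7.2 (Planned Analyses) specifies a mixed model with a random intercept for A1C at baseline, 3 and 6 months. On its estimand it says: "The slope of time will represent the average change of A1C over 6 months".

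**The concern.** For a within-person change, the SD of the difference is fixed by the SDs at the two visits and their correlation. A correlation of 0.57 is only a little above 0.5, the value at which the SD of change equals the single-visit SD when the two SDs are equal. The SD of change should therefore be slightly below 1.2. A value of 0.72 is far too small.

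A1C is one of two primary outcomes, and section 3.3 makes estimating the effect size the primary objective of Phase 2. The documents state no hypothesis and no power target, so the ±0.27% margin is the whole quantitative account of what 30 participants can deliver on A1C. If it is wrong, readers are promised a clearly tighter estimate than the plan's own inputs support. Section 7.1 also says the pilot is to supply preliminary data for a larger study. Anyone who carried 0.72 forward as a planning SD would understate variance, and hence sample size, by a factor of (1.113/0.72)² = 2.39.

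**Working it through.** **Inputs, all from section 7.1:** SD of A1C 1.2; correlation r = 0.57; n = 30; two-sided 95% confidence. The 97.5% t quantile on 29 df is 2.045.

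**Step 1. Reproduce the plan from 0.72 onward.**
- SE = 0.72/sqrt(30) = 0.131, stated as 0.13.
- Margin = 2.045 × 0.1315 = 0.269, stated as 0.27. (The normal quantile, 1.960, would give 0.258, so the plan used t.)

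These steps are sound. The break comes before them, between the pair (1.2, 0.57) and 0.72.

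**Step 2. SD of change from the stated inputs, with equal SDs.** Section 7.1 gives only one SD, so I assume it applies at both visits.
- SD of change = 1.2 × sqrt(2 × (1 − 0.57)) = 1.2 × sqrt(0.86) = 1.113
- SE = 1.113/sqrt(30) = 0.203
- Margin = 2.045 × 0.203 = ±0.416% (±0.398% with the normal quantile)
- Ratio to the plan: 1.113/0.72 = 1.55

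**Step 3. Relax the equal-SD assumption.** In general, SD of change = sqrt(s1² + s2² − 2 × r × s1 × s2). With s1 = 1.2 and r = 0.57, this is smallest at s2 = 0.57 × 1.2 = 0.684, where it equals 1.2 × sqrt(1 − 0.57²) = 0.986. The margin there is ±0.368%, still 0.986/0.72 = 1.37 times the stated width. For an assumed 6-month SD between 0.8 and 1.6, the SD of change runs from 0.99 to 1.35 and the margin from ±0.37% to ±0.50%. No second SD gives 0.72.

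**Step 4. Other readings.**

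| Reading | SD | 95% margin (t) |
|---|---|---|
| Plan as stated | 0.72 | ±0.27 |
| Paired change, equal SDs | 1.113 | ±0.416 |
| Adjusted for baseline, 1.2 × sqrt(1 − 0.57²) | 0.986 | ±0.368 |
| 1.2 is a variance, sqrt(1.2 × 0.86) | 1.016 | ±0.379 |
| Mean of the two follow-ups minus baseline, 1.2 × sqrt(1.5 × 0.43) | 0.964 | ±0.360 |
| Factor 2 omitted (not an SD of change), 1.2 × sqrt(0.43) | 0.787 | ±0.294 |

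**Step 5. The planned mixed model.** With a random intercept, correlation 0.57 and complete data at 0, 3 and 6 months, the residual variance is 1.44 × 0.43 = 0.619. The squared deviations of time sum to 9 + 0 + 9 = 18. The variance of 6 × slope is 36 × 0.619/(18 × 30) = 0.0413, so its SE is 0.203, the same as for the paired change. The margin is ±0.416% on 29 df or ±0.407% on 59 df. The 3-month visit does not recover the stated precision.

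**Step 6. What would make 0.72 right.** With SD 1.2 at both visits, r would have to be 1 − 0.72²/(2 × 1.44) = 0.82. With r = 0.57, the common SD would have to be 0.72/sqrt(0.86) = 0.78. With the stated inputs, a margin of ±0.27% would need about 68 completers.

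**The case against.** There are two fair objections. The first is that the documents show only that 1.2, 0.57 and 0.72 cannot all be right; they do not show which is wrong. The source study is not available here. 0.72 might be a change SD observed in it, with 1.2 or 0.57 misprinted or taken from a different subset. This stands as a limit on the diagnosis: the ±0.42% figure depends on both inputs being correct. It does not rescue the paragraph, which presents 0.72 directly after 1.2 and 0.57 with nothing else to support it. At least one of the three figures has to change.

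The second is that little depends on the margin. The sample of 30 is a feasibility choice, section 3.2 specifies no hypotheses for Phase 2, no decision rule uses ±0.27%, there is no interim analysis, and the final interval will come from observed data. This also stands. It limits the harm to an overstated precision claim, but the claim is still wrong as written and concerns a primary outcome.

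**Conclusion.** The concern holds. From the plan's own SD and correlation, 30 completers give an SD of change of about 1.11, an SE of 0.20 and a 95% margin of about ±0.42% A1C, against the stated 0.72, 0.13 and ±0.27%. The true margin is about 55% wider than stated. These values assume equal SDs at the two visits, complete data and a t quantile on 29 df. The conclusion does not rest on equal SDs: if either visit has SD 1.2 and the correlation is 0.57, the margin cannot be below about ±0.37%. The SE and margin are wrong only because they inherit 0.72. Neither the sample size of 30 nor the planned analysis is invalidated.

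**What to change.** Keep n = 30 and the section 7.2 analysis. In section 7.1, check 1.2, 0.57 and 0.72 against the source data, then do one of the following:

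- If 1.2 and 0.57 are correct, show the formula, state the equal-SD assumption, and restate the figures: SD of change 1.2 × sqrt(2 × (1 − 0.57)) = 1.11, SE 0.20, 95% margin about ±0.42% A1C with 30 completers.
- If 1.2 or 0.57 is a misprint, correct that input and show the calculation that leads to the SD of change.

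Optionally, add the margin under an explicitly assumed loss to follow-up, since the documents give no retention figure. At an SD of change of 1.11, a paired analysis gives about ±0.44% with 27 completers, ±0.47% with 24 and ±0.51% with 21. The mixed model would do somewhat better where lost participants have a 3-month value, because it keeps them: "The GLMM will include all participants with data at baseline and at least one of post-intervention value".

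The cost is a short rewording of one paragraph and a less favourable precision statement. No participants are added and no analysis changes.

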In Phase 2, we will use a pre-post design, collecting data from participants at baseline, 3 and 6 months. We will evaluate change over time in participants.

Study Design:

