5.2 Number of Participants

For Phase 1, we will recruit health care providers (n=5), CHWs, (n=2), and adults with T2D (n=5), at each clinical site (total sample: 10 providers, 4 CHWs, and 10 adults with T2D).

For Phase 2, we will recruit 30 adults with T2D (n=15 from each clinic).

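### The ±0.27% A1C margin in Section 7.1 is a best case: it takes all 30 people enrolled to have complete baseline-to-6-month A1C, with no allowance for loss

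*Combined protocol and SAP*

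**What the plan says.** Section 7.1 builds the precision statement in four steps. From an earlier study, "we obtained a standard deviation of 1.2 and a sample correlation of 0.57 in repeatedly measured A1C over 6 months". Then "The estimated standard deviation of changed A1C will be 0.72", and "the sample size of 30 will produce a standard error of 0.13". Finally, "the proposed sample size of 30 could estimate a change of A1C over time with a margin of" ±0.27%. The paragraph presents 30 as a feasible size for a pilot meant to inform a larger study. It gives no expected retention and does not say that the margin depends on full follow-up.

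Thirty is also the enrolment target in Section 5.2: "For Phase 2, we will recruit 30 adults with T2D (n=15 from each clinic". Section 4 describes "collecting data from participants at baseline, 3 and 6 months".

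Other sections allow for gaps. Section 7.2 says "The GLMM will include all participants with data at baseline and at least one of post-intervention value", with missing values handled by maximum likelihood. Sections 7.2 and 7.7 add a rerun with multiple imputation. Section 6.1 lists retention measures and Section 6.5 covers withdrawal. Section 6.6 allows telehealth for questionnaires, but A1C has to be taken at the clinic or another private place. No section gives an expected loss rate.

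**The concern.** The same number, 30, serves as both the enrolment target and the divisor in the standard error. The margin therefore holds only if nobody lacks a 6-month A1C, while the analysis sections are written for the case where some do. A reader of 7.1 cannot tell that ±0.27 is the most favourable value.

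A1C is one of the two primary outcomes, and this margin is the only precision figure given for 30 participants. The pilot's purpose is to supply estimates for a larger study, so its readers should see the precision to expect from the people likely to be followed up.

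**Working it through.** **Inputs.** From 7.1: SD 1.2, r 0.57, stated SD of change 0.72, n = 30, 95% interval (taken as two-sided). From 7.2: random intercept, linear time, and inclusion of anyone with baseline and at least one later value. Assumption, because the documents give no rate: 10–20% of 30, that is 3 to 6 people, lack a 6-month A1C.

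**1. Reproduce the plan's figure.** Margin = t(0.975, n−1) × SD of change/√n. SE = 0.72/√30 = 0.1315, and 2.045 × 0.1315 = 0.269. This is the printed ±0.27. With the normal quantile it would be 0.258, so the plan used t with 29 degrees of freedom, which means 30 complete pairs.

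**2. People without a 6-month value have no post-baseline value at all.** Section 7.2 then leaves them out, and complete pairs remain.
- 29 pairs: ±0.274, which still rounds to 0.27.
- 27 pairs: 0.72/√27 = 0.1386; × 2.056 = ±0.285; 0.285/0.269 = 1.06.
- 24 pairs: 0.72/√24 = 0.1470; × 2.069 = ±0.304; 0.304/0.269 = 1.13.

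The SE alone grows by √(30/27) = 1.05 and √(30/24) = 1.12. The rest comes from the larger t quantile. These ratios are the same for any SD of change.

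**3. They still have a 3-month value, so the planned model keeps them.** Code time as 0, 0.5 and 1, with equal correlation r between visits. Each person with m visits contributes X′(I − cJ)X to the information, in units of 1/[SD²(1−r)], where c = r/(1−r+mr). At r = 0.57:
- Three visits (c = 0.266): intercept 0.603, cross term 0.301, slope 0.651.
- Baseline and 3 months only (c = 0.363): 0.548, 0.137, 0.159.

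Sum over people; the slope information is slope − cross²/intercept:
- 30 complete: 15.00. Here the SE equals the SD of change/√30, as in step 1.
- 27 complete + 3 partial: 13.97. SE ratio √(15/13.97) = 1.04.
- 24 complete + 6 partial: 12.92. SE ratio √(15/12.92) = 1.08.

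On the stated 0.72 this gives about ±0.28 and ±0.29, using t with 29 degrees of freedom. Using r = 0.82 instead, the correlation that 0.72 would imply at SD 1.2, leaves the ratios at 1.04 and 1.08.

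**4. The stated SD of change.** SD × √(2(1−r)) = 1.2 × √0.86 = 1.113, not 0.72. To obtain 0.72 one would need r = 0.82 at SD 1.2, or SD = 0.776 at r = 0.57.

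**5. Margins side by side**

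| 6-month A1C available | SD of change 0.72, planned model | 0.72, complete pairs | 1.113, planned model | 1.113, complete pairs |
|---|---|---|---|---|
| 30 | ±0.269 | ±0.269 | ±0.416 | ±0.416 |
| 27 | ±0.279 | ±0.285 | ±0.431 | ±0.440 |
| 24 | ±0.290 | ±0.304 | ±0.448 | ±0.470 |

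The planned-model columns suppose that everyone without a 6-month value has a 3-month one, and use r = 0.57.

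**The case against.** The last step of 7.1 contains no miscalculation: 0.72, 30 and the t quantile do give 0.27. What is missing is an allowance for loss.

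A reader might infer that 30 enrolled will fail to reach the stated precision because of dropout. The documents do not support that. They give no loss rate, and retention measures and a missing-data method are routine provisions that do not predict loss of any particular size. One lost pair leaves the rounded figure unchanged, and the mixed model recovers part of what a missed 6-month visit costs. The width finally reported also depends on the observed SD, whose own relative sampling error is about 1/√58 = 13%. If 0.72 were the true SD, the interval would come out no wider than ±0.269 with probability about 53% with 30 pairs, 38% with 27 and 24% with 24, from P(χ² with n−1 df ≤ (n−1)(0.269√n/(0.72t))²).

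A reader might also infer that the margin determined the sample size, so that enrolment has to rise. Section 7.1 calls 30 feasible and sets no precision target, and Section 3.2 states that Phase 2 has no specified hypotheses. Enlarging for dropout alone, to 34 at 10% loss or 38 at 20%, would not restore ±0.27 on the stated SD and correlation either: that takes 68 complete pairs.

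All of this stands. It limits the point to how the margin is stated. It does not remove it, because 7.1 still gives a full-follow-up figure without saying so.

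**Conclusion.** The point holds as a matter of disclosure. The ±0.27 margin assumes 30 complete baseline-to-6-month pairs from 30 people enrolled, and 7.1 does not say so although 7.2 and 7.7 provide for missing A1C.

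At an assumed 10–20% missing at 6 months, the cost runs from a 4–8% larger SE (all of them with a 3-month value, planned model) to a 6–13% wider margin (none with a post-baseline value). On the stated 0.72 that is about 0.01 to 0.035 percentage points of A1C. The calculation takes equal correlation between visits and does not address loss related to outcome.

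The mismatch in the SD of change is larger: ±0.416 against ±0.269 with no loss at all, about 55% wider. Correcting it does not settle the loss question, since the proportional widening is essentially the same on either SD. Neither issue is a case for more participants.

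**What to change.** In Section 7.1, in this order:

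1. Reconcile the SD of change with its inputs. Either correct 0.72 to the value that SD 1.2 and r 0.57 imply (1.113), or correct the SD or correlation and give the source.
2. Say that the margin assumes a 6-month A1C from all 30 participants.
3. State the number expected to have a 6-month A1C, with its basis, and give the margin for that number as a range: the planned random-intercept model with 3-month values present at one end, complete pairs only at the other. If no retention figure is available, show 27 and 24 as illustrations and label them as assumptions.

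Keep enrolment at 30. The cost is a sentence or two and a slightly less favourable stated margin, with no change to visits or analysis.

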7.2 Planned Analyses

Phase 1 analysis:

The sample of participants in the interviews/focus groups will be described using frequency distributions and appropriate summary statistics (SAS version 9.4). Content analysis will be used to analyze qualitative data from each type of stakeholder along with field notes and interviewer observations (Hsieh, 2005) Rigor for this process includes: (a) transcribing taped interviews; (b) checking transcripts against tapes for accuracy; (c) developing coding categories by two members of the research team; (d) assigning codes of text with appropriate checks; (e) reviewing coded data to identify themes across participants; and (f) a team approach to data analysis. At research team meetings we will assess researcher bias, coding saturation, and interpretative congruence. Results will be used to finalize the intervention protocol for implementation in Phase 2

Phase 2 Analysis: Data will be collected in the form of questionnaires online on the secure REDCap system. A1C data, electronic medical record data and patient portal data will be entered into REDCap or Excel and merged into one database. All data that are downloaded from REDCap or Excel will be onto a Yale server, which has several secure firewall systems. Descriptive analyses will be performed to assess demographic and clinical characteristics of the sample. Feasibility data will be summarized. Distributions of outcome variables will be examined for central tendency and dispersion. We will estimate the Cohen's D effect size of MAP on A1C and will examine the intervention effect over 6 months using generalized linear mixed model (GLMM) with random intercept, which will incorporate the correlation within repeatedly measured A1C. The slope of time will represent the average change of A1C over 6 months. The GLMM will include all participants with data at baseline and at least one of post-intervention value and will handle missing data using maximum likelihood approach. To confirm findings with missing data, we will rerun the GLMM with multiple imputations which will be produced by assuming multivariate normal distribution of repeatedly measured A1C. Number of logins and the repeatedly measured secondary outcomes will be analyzed with the same approach using the GLMM. Residuals will be assessed for normality assumption and

variables will be transformed with an appropriate form when the normality assumption does not hold. Count data such as portal use, clinic appointments, ER visits, and hospitalizations will be modeled using Poisson or Negative Binomial regression model. For exceeding zero count (i.e. a high proportion of no appointment, ER visit, hospitalization), zero-inflated regression models will be employed. We will also estimate the effects of portal use (frequency, type) and feasibility factors (e.g., acceptability, attendance, fidelity) on A1c at 6 months after controlling for baseline A1c using generalized linear model (GLM). For future research with a large sample size, we will obtain an effect size (partial eta square) of each factor from GLM. Qualitative data will be analyzed using the aforementioned content analysis approach.

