5.3 Eligibility Criteria

Phase 1 eligibility criteria for adults with T2D

In order to be eligible for inclusion in the study, an individual must meet all of the following criteria:

- Established patient of one of the partner CHCs;
- Age ≥ 18 years;
- Diagnosed with T2D ≥ 6 months;
- Able to read in English or Spanish.

Any individual who meets any of the following criteria will be excluded from participation in this study:

Cognitive impairment (≥ 3 errors on the Six Item Screener for cognitive impairment in clinical research [SIS]) (Callahan et al. 2002) as they will have difficulty in completing the study requirements

Gestational diabetes

Diagnosis of type 1 diabetes

Phase 1 eligibility criteria for health care providers

In order to be eligible for inclusion in the study, an individual must meet all of the following criteria:

Health care provider or community health worker at one of our partner CHC

Provides care/services for adults with T2D

Any individual who meets any of the following criteria will be excluded from participation in this study:

None

Vulnerable/special populations that will be included are: economically or educationally disadvantaged populations and elderly populations (who do not demonstrate cognitive impairment). These groups have health disparities with respect to patient portal use and are important to include in the research to be able to address their needs and improve health equity and health outcomes.

Phase 2: Inclusion criteria are: established patient of one of the partner CHCs; age 18 years or older; diagnosed with T2D >6 months; most recent A1C >7.5%; no current use of patient portal, no intention of moving/changing clinic within 6 months; and able to read in English or Spanish. Exclusion criteria include: cognitive impairment and gestational diabetes.

Participants who participated in Phase 1 will be eligible to participate in Phase 2.

Vulnerable/special populations that will be included are: economically or educationally disadvantaged populations and elderly populations (who do not demonstrate cognitive impairment). These groups have health disparities with respect to patient portal use and are important to include in the research to be able to address their needs and improve health equity and health outcomes.

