7.7 Handling of Missing Data

Phase 1: Not applicable

Phase 2: To confirm findings with missing data, we will rerun the GLMM with multiple imputations which will be produced by assuming multivariate normal distribution of repeatedly measured A1C. Number of logins and the repeatedly measured secondary outcomes will be analyzed with the same approach using the GLMM.

8 Data/Specimen Handling and Record Keeping

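### The A1C model has a random intercept only, so its confidence interval for the 6-month change is too narrow if A1C values 6 months apart correlate less than values 3 months apart

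*Combined protocol and SAP*

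**What the plan says.** Section 7.2 (Phase 2 Analysis) names Cohen's D for A1C and then a "generalized linear mixed model (GLMM) with random intercept, which will incorporate the correlation within repeatedly measured A1C". The summary of change is the linear time coefficient: "The slope of time will represent the average change of A1C over 6 months". No random slope, serial or unstructured residual covariance, robust standard error or comparison of covariance structures is named. The stated model check concerns distribution shape ("Residuals will be assessed for normality assumption and", with transformation where normality fails). The missing-data sensitivity analysis in Section 7.7 refits the same model: "we will rerun the GLMM with multiple imputations which will be produced by assuming multivariate normal distribution of repeatedly measured A1C".

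The only information on correlation is in Section 7.1: an SD of 1.2 and "a sample correlation of 0.57 in repeatedly measured A1C over 6 months". No separate 3-month value is given. Section 3.3 makes the effect size on portal logins and A1C the Phase 2 objective. Section 7.1 justifies n = 30 by the width of a 95% interval for A1C change. Section 3.2 states that Phase 2 has no specified hypotheses.

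**The concern.** A random intercept with independent residuals forces the 0–3, 3–6 and 0–6 month pairs to share one correlation. Repeated biological measurements often correlate less as the gap between them grows. If A1C does so here, the 0–6 month change varies more than the model believes, and the reported interval is too short. Neither planned safeguard addresses this. A normality check says nothing about lag correlation, and the imputation rerun ends in the same random-intercept model.

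What is at stake is the precision attached to the A1C change that is meant to inform a larger study. The complete-data point estimate is not at issue. Nor is Cohen's D if it uses the observed SD of change; Section 7.2 does not say which SD it will use.

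**Working it through.** **The plan's own figure.** Section 7.1 states: "The estimated standard deviation of changed A1C will be 0.72 and the sample size of 30 will produce a standard error of 0.13". From 0.72, 0.72/√30 = 0.131, and 2.045 × 0.131 = 0.269, which matches the stated ±0.27. But SD 1.2 and r = 0.57 give an SD of change of 1.2 × √(2 × 0.43) = 1.11, an SE of 1.11/√30 = 0.203 and a margin of 2.045 × 0.203 = ±0.42. An SD of 0.72 would need r = 0.82. That conflict is a separate matter; the calculations below use 1.2 and 0.57.

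**Inputs.** From the plan: n = 30, visits at 0, 3 and 6 months, SD 1.2, r = 0.57. Assumed: equal SDs, linear mean change, complete data, r03 = r36 = r3, and the lag pattern.

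**Formula.** With three equally spaced visits and complete data, the slope over 6 months equals the mean of (month 6 − baseline).
- True variance: 2·SD²·(1 − r06)/n.
- Variance the model reports, approximately: 2·SD²·(1 − r̄)/n, where r̄ = (2·r3 + r06)/3.
- Ratio of model SE to true SE: √[(1 − r̄)/(1 − r06)]. This is below 1 whenever r06 < r3, and it does not depend on the SD.

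**Worked case**, with 0.57 as the 0–6 month value and exponential decay: r3 = √0.57 = 0.755 and r̄ = (1.510 + 0.57)/3 = 0.693. The ratio is √(0.307/0.43) = 0.84, so the model reports an SE of about 0.172 where the true value is 0.203.

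**Simulated coverage of the nominal 95% interval** (200,000 runs per case; 59 df for the random-intercept model). Because 0.57 can be read in three ways, each is shown:

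| Assumed pattern | 0.57 = 0–6 month value | 0.57 = average of pairs | 0.57 = 3-month value |
|---|---|---|---|
| Equal correlation | 95% | 95% | 95% |
| Halfway: r3 / r06 | 0.6625 / 0.57: 93.1% | 0.608 / 0.494: 92.9% | 0.57 / 0.447: 93.0% |
| Exponential: r3 / r06 | 0.755 / 0.57: 90.1% | 0.646 / 0.418: 90.7% | 0.57 / 0.325: 91.2% |

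The SE ratio is 0.92 to 0.93 halfway and 0.84 to 0.87 under exponential decay. Under the first reading the average half-width of the planned interval is 0.405, 0.374 and 0.340 A1C points for the three patterns. A paired 0–6 month contrast averages 0.412 and covers 95% throughout.

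REML fits of the random-intercept model to 500 simulated data sets (first reading, exponential decay) gave a reported SE of 0.172 against an empirical 0.210, with 90% coverage.

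**Departures from these assumptions.**
- *Curved change* (0/−0.5/−0.5): the lack of fit enters the residual and widens the interval slightly. The exponential figures become 91.0, 91.3 and 91.7%.
- *Line or covariance?* With visit as a category but still a random intercept only, coverage is 90.3% (first reading, exponential, curved change). The covariance drives the shortfall.
- *Unequal SDs*: the entry rule ("most recent A1C >7.5"%) may shrink the baseline SD. At an assumed 1.0 or 0.9, the 90.1% becomes 91.0 or 91.5%. At an assumed 1.4 it becomes 89.5%.
- *Dropout*: with an assumed 20% random loss after month 3, the same curved change and the first reading with exponential decay, the planned slope averages −0.53 against a true −0.50 and covers 90.8%. The imputation rerun averages −0.50 and covers 92.2%; it covers 94.4% halfway and 95.7% with equal correlations. Under the exponential pattern, an unstructured-covariance estimate covers 95.6%.

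**The case against.** The strongest reply is that the condition has no support in the documents. One correlation is given, it can be read as common to all pairs, and then the planned interval is right. If the 6-month pair correlated more than the 3-month pairs (0.65 against 0.57), the interval would be too wide, with about 96% coverage. This stands: every equal-SD shortfall above depends on an assumed pattern.

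Pure exponential decay is also toward the pessimistic end, because a fingerstick assay carries measurement error that does not depend on lag. With r06 = 0.57, adding such error at assumed reliabilities of 0.95, 0.90, 0.85 and 0.80 gives coverage of about 90.8, 91.4, 92.2 and 92.8%. About 93% is a fair middle value. The exponential figures are not a strict lower limit either, as the 1.4 SD case shows.

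It can also be said that Section 7.2 does not exclude a residual covariance structure, that it names no interval for the slope, and that the main deliverable may be a Cohen's D that this does not touch. The first is fair, but with nothing else named, random-intercept-only is the natural reading. The other two limit the stakes and leave the mechanism intact.

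Finally, categorical visits are not needed to repair the interval; the covariance alone would do that. This is correct. The categorical form is recommended because it also shows the 3-month change, which a single slope hides.

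**Conclusion.** The concern holds as a conditional one. The specified model builds in equal correlation, and nothing in the plan tests or relaxes it. If A1C correlation falls with lag, the interval for the 6-month change is too short. Coverage is about 93% in a middle case and 90 to 91% under exponential decay, for n = 30 with complete data, equal SDs and a linear mean. If 0.57 applies to every pair, the planned interval is correct.

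The complete-data estimate is unaffected. With dropout and a curved change there is a slight bias (−0.53 against −0.50 in the assumed case), which the imputation rerun largely removes; the rerun corrects the standard error only partly. In a pilot with no specified hypotheses and no decision rule tied to this interval, this is a low-priority improvement, worth making because it is cheap.

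**What to change.** In Section 7.2, fit visit (0, 3, 6 months) as a category with an unstructured 3×3 covariance, REML and Kenward-Roger degrees of freedom. Report the baseline-to-6-month contrast as the main A1C estimate, with the 3-month contrast beside it, and keep the linear slope as a supplementary summary. In Section 7.7, use the same model for the multiple-imputation rerun. If the team prefers to keep the slope as the main summary, a small-sample-corrected robust standard error would address the interval alone.

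The cost is a few lines of specification and no new data. The model gains one mean parameter and four covariance parameters. If the correlations are in fact equal, the average half-width rises from 0.405 to 0.412 A1C points (under 2% wider, at SD 1.2 and r = 0.57). Naming the covariance before the data are seen also avoids a data-driven choice.
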